1.1.5 Endocrine Therapy for Surgically Treated Ductal Carcinoma in situ

There is evidence from one placebo-controlled trial, NSABP B-24 (23), that in patients treated for DCIS with lumpectomy and adjuvant radiotherapy, tamoxifen reduces the risk of ipsilateral local recurrence by 30% and of contralateral breast cancer by 50% (24). The absolute risk at 5 years of any (invasive or non-invasive) breast cancer event is small (tamoxifen arm 8% and placebo arm 13%). Survival was not influenced by treatment. A subsequent randomised controlled trial with a more complex design (25, 26) examined the use of tamoxifen versus no adjuvant therapy following complete local excision of DCIS in the absence or presence of radiotherapy. In the absence of radiotherapy, tamoxifen was again associated with a 30% overall reduction in breast events through reduction in DCIS recurrence and contralateral DCIS and invasive disease events. Tamoxifen was however ineffective in preventing ipsilateral invasive recurrence. In the presence of radiotherapy, tamoxifen appeared ineffective. Survival was not impacted by radiotherapy or tamoxifen in this trial, with breast cancer accounting for only 20% of all deaths (2% breast deaths and 11% overall deaths).

Recent data from two trials (IBIS II DCIS and NSABP B-35) comparing tamoxifen and the aromatase inhibitor anastrazole have reported no difference or a slight reduction in breast cancer events with anastazole. No survival differences have been observed but follow up is short (27, 28).

National Institute for Health and Care Excellence (NICE) guidelines for familial breast cancer state "Do not offer adjuvant tamoxifen after breast conserving surgery to patients with DCIS" (29).

There is sparse data regarding endocrine treatment alone for DCIS. Data presented at the San Antonio Breast Cancer Symposium in 2011 showed a decrease in subsequent breast events in patients with all types of atypia, including DCIS. This was a retrospective study, including symptomatic patients and was not restricted to large volume biopsies (30). The role of endocrine therapy in asymptomatic, surgically untreated, low risk DCIS, remains unknown and of unproven long term utility. Endocrine therapy is associated with significant and persistent side effects.

Page 3 of 48 Version 4.0, 15th March 2016

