2.2.2 Outcome Measures of Main Trial

2.2.2.1 Primary Outcome

Ipsilateral invasive breast cancer free survival time: defined in whole days measured as time from randomisation until first report of ipsilateral invasive breast cancer or death (from any cause), whichever happens first. Patients who withdraw or who are lost to follow-up will be censored at the date last known to be alive and free of disease. Patients not having an event at the time of analysis will be censored at the date last seen alive and free of disease.

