16.2.2 Analysis of Outcome Measures

The primary research question to be addressed by this analysis asks if active monitoring for newly diagnosed, asymptomatic, low grade DCIS is non-inferior in terms of ipsilateral invasive breast cancer survival time when compared to surgical intervention to remove all traces of DCIS at diagnosis.

The primary aim is to test the null hypothesis that active monitoring of women diagnosed with low risk DCIS is not non-inferior in terms of invasive breast cancer free survival time compared to treatment with surgery. Invasive breast cancer survival time will be compared across the two arms on a per protocol and intent-to-treat basis, using a 1-sided (5% significance level) log-rank test for non-inferiority and a hazard ratio with a one-sided 95% confidence interval.

There is very little relevant evidence of the actual ipsilateral invasive breast cancer rate amongst low risk DCIS patients and an event rate of 2.5% at 5 years reflects current evidence (26). A difference in invasive breast cancer survival of no more than 2.5% is judged as clinically acceptable both by the TMG and the wider breast cancer clinical community. This gives a non-inferiority margin for the trial defined as an absolute reduction in the 5 year ipsilateral invasive breast cancer free survival rate at 5 years of 2.5% i.e. from 97.5% to 95% and this equates to a hazard ratio of HR=2.02 . Models for survival data will be considered to take into account the stratification factors and other potentially important prognostic factors.

All analyses will be carried out for both per protocol and intent to treat study populations. The primary and secondary outcomes will be calculated for all patients and compared between treatment groups. Time to event outcomes will be calculated for all patients and methods described by Kaplan and Meier used to present survival curves. The log-rank statistic will be used to test hypotheses.

Results from the Brief COPE will allow us to dichotomise women into two groups, those who manage a situation using a problem focused approach and those who have a detached method of coping.

The STAI permits us to measure changes in state anxiety over time. We will examine changes using Analysis of Covariance (ANCOVA) with baseline trait and state anxiety as covariates.

Page **35** of **48** Version 4.0, 15th March 2016

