16.2.6 Sample Size Justification

The sample size calculation is based on the primary outcome of ipsilateral invasive breast cancer survival time. The primary analysis will be a comparison of the ipsilateral invasive breast cancer free rate between the Active Monitoring arm and Surgery Arm using a log-rank test for non-inferiority. The justification for the sample size is explained below.

Taking into account all published 5 year recurrence rates post-surgery for low risk disease, excluding contralateral disease and ipsilateral *in situ* disease, the projected recurrence rate (ipsilateral invasive breast cancer rate) at 5 years in the Surgery Arm is 2.5%. There is no relevant published data on 5 year ipsilateral invasive cancer rate in non-operated asymptomatic mammogram-detected low risk DCIS diagnosed by VACB and centrally reviewed. We have therefore based our non-inferiority calculation on extrapolation from the surgical data, estimates of overtreatment and what is judged to be a clinically relevant non-inferiority margin.

Page **36** of **48** Version 4.0, 15th March 2016

The non-inferiority design aims to show that not treating low risk DCIS with surgery is no worse (than a given margin) than treating with surgery. The primary outcome is ipsilateral invasive breast cancer free survival time and we will use a log-rank test for non-inferiority to determine whether no surgery is as good as surgery in these low risk DCIS patients by comparing the survival distributions of the two treatment groups. Because of the directional nature of the hypothesis, this non-inferiority test is one-sided. Jung *et al.* (49) derived an asymptotically exact sample size formula for the non-inferiority log-rank test to give the number of patients required to reject the null hypothesis that no surgery is worse than surgery, based on a given level of power and significance, assuming exponential survival distributions for both treatment groups, uniform patient accrual during a specified accrual period and set number of events during a period of follow-up, uniform censoring and no loss to follow-up.

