The one-sided Type I error rate is set at 5% and Type II error rate set at 20%, giving 80% power. The accrual period will be over 6 years and patients will be in follow-up for 5 years. The ipsilateral invasive breast cancer free rate at 5 years, based upon previous data (see above), is estimated to be 97.5%. The non-inferiority margin of maximal difference is determined to be 2.5%, therefore if the invasive breast cancer free rate at 5 years in the untreated group is not worse than 95%, then non-inferiority would be concluded since it falls within 2.5% of the treated population's invasive breast cancer free survival rate (97.5%). This decision was reached by the TMG, which comprises clinicians and patient representatives as well as statisticians. This non-inferiority margin equates to a hazard ratio of 2.02

The sample size calculation, given the above information estimates that 50 events will be sufficient to answer robustly the primary research question and it is estimated that 932 patients are required to achieve this number of events allowing for a 10% loss to follow-up/non-adherence rate.

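### The primary endpoint counts death from any cause, but the 97.5% control rate, the 2.5-point margin, HR 2.02, 50 events and 932 women were derived from invasive recurrence alone, so the forms of the margin no longer agree

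*Protocol*

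**What the plan says.** Section 2.2.2.1 measures the primary outcome from randomisation "until first report of ipsilateral invasive breast cancer or death (from any cause), whichever happens first". Time to ipsilateral invasive breast cancer without death is the first secondary outcome (section 2.2.2.2).

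The design figures come from recurrence. In section 16.2.6, "the projected recurrence rate (ipsilateral invasive breast cancer rate) at 5 years in the Surgery Arm is 2.5" (per cent), taken from published post-surgery results. The same section continues: "The ipsilateral invasive breast cancer free rate at 5 years, based upon previous data (see above), is estimated to be 97.5" (per cent). Section 16.2.2 sets the margin as an "absolute reduction in the 5 year ipsilateral invasive breast cancer free survival rate at 5 years of 2.5% i.e. from 97.5% to 95" (per cent), and section 16.2.6 adds: "This non-inferiority margin equates to a hazard ratio of 2.02". A third form of the criterion also stands in 16.2.6: "if the invasive breast cancer free rate at 5 years in the untreated group is not worse than 95%, then non-inferiority would be concluded". On error rates: "The one-sided Type I error rate is set at 5% and Type II error rate set at 20%, giving 80% power". The result is 50 events and 932 women, with 10% allowed for loss or non-adherence.

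The test is a one-sided 5% log-rank test for non-inferiority with a one-sided 95% confidence limit for the hazard ratio (section 16.2.2). It is timed by follow-up, when every patient has at least five years (section 16.2.5), and not by an event count.

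**The concern.** The 2.5% is a recurrence rate and contains no deaths. The endpoint that will be tested does contain them, in women aged 46 or over with no upper age limit (section 4.1) and with a stratum above 65 (section 6.2.2). So the control arm will not be at 97.5% on the tested endpoint, and HR 2.02 will not correspond to a loss of 2.5 points.

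In a non-inferiority trial this matters because events unrelated to the treatment choice dilute the hazard ratio, and dilution favours the experimental arm. At stake is a conclusion that Active Monitoring is non-inferior when the invasive cancer rate lies outside the difference the Trial Management Group judged acceptable. The endpoint, margin and sample size are all fixed in the protocol, so an analysis plan alone cannot repair the mismatch.

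**Working it through.** **Inputs from the protocol.** 97.5% v 95% at five years; HR 2.02; one-sided 5%; 80% power; 1:1 allocation; uniform accrual over 6 years plus 5 years of follow-up, hence 5-11 years per woman; 932 × 0.9 = 839 evaluable.

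**Assumed.** Exponential times, and a death hazard d equal in both arms of 0.3-1.0% per year (1.5-4.9% at five years). A row at 1% five-year mortality tests a lower value.

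**Step 1: reproduce the plan without deaths.**
- Hazards: hS = -ln(0.975)/5 = 0.005064 and hA = -ln(0.95)/5 = 0.010259 per year. Ratio 2.026 (the protocol gives 2.02).
- Events: 4(1.645 + 0.842)²/(ln 2.02)² = 24.73/0.4943 = 50.0; at the unrounded 2.026, 49.6.
- Event probability: 1 - [exp(-5h) - exp(-11h)]/(6h) = 0.0397 and 0.0786, mean 0.0592. Then 49.6/0.0592, with unrounded figures, is 838.6 women, and 838.6/0.9 = 932.

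All the design figures come out of recurrence alone.

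**Step 2: add deaths.**
- Composite HR with invasive cancer at 2.5% v 5%: (hA + d)/(hS + d).
- Chance of declaring non-inferiority, with D events: Φ[(ln 2.02 - ln HR)·√D/2 - 1.645].
- Invasive HR that a composite HR of 2.02 allows: [2.02(hS + d) - d]/hS.
- Excess: difference in five-year cumulative incidence, h/(h + d)·[1 - exp(-5(h + d))].

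Example, d = 0.005: HR = 0.015259/0.010064 = 1.516; D = 80; Φ[(0.7031 - 0.4163)·√80/2 - 1.645] = 0.36. Allowed invasive HR = (2.02 × 0.010064 - 0.005)/0.005064 = 3.03.

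| Deaths per year | Deaths at 5 y | Composite HR | Events | P(non-inferiority) | Invasive HR allowed | Excess, points |
|---|---|---|---|---|---|---|
| 0 | 0% | 2.03 | 50 | 5% | 2.02 | 2.5 |
| 0.2% | 1.0% | 1.73 | 62 | 15% | 2.42 | 3.4 |
| 0.3% | 1.5% | 1.64 | 68 | 21% | 2.62 | 3.9 |
| 0.5% | 2.5% | 1.52 | 80 | 36% | 3.03 | 4.8 |
| 0.75% | 3.7% | 1.41 | 95 | 54% | 3.53 | 5.9 |
| 1.0% | 4.9% | 1.34 | 110 | 69% | 4.03 | 7.0 |

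A Cox-model simulation (3,000 trials of 838 women) gave 15% at 1% five-year mortality and 68% at 5%; the formula gives 15% and 70%.

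**Step 3: the other two forms of the margin.** With invasive cancer at 2.5% v 5%, the five-year composite difference is 96.1% v 93.6% (2.46 points) at 0.3% per year and 92.7% v 90.4% (2.38 points) at 1.0%. The absolute difference hardly moves. Against a literal 95% floor, an Active Monitoring arm with no invasive excess at all would stand at 96.1%, 95.1% and 92.7% for 0.3%, 0.5% and 1.0% per year, so at the upper end it would fail.

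**Step 4: what each remedy would state.**
- Invasive cancer alone, both arms at 97.5%: 839 × 0.0397 = 33 events, slightly fewer once deaths remove women from risk. Power = Φ(0.7031·√33.3/2 - 1.645) = 65%.
- Composite kept: control five-year rate S = exp[-5(hS + d)] = 96.1% to 92.7%. HR matching 2.5 points = ln(S - 0.025)/ln S = 1.65 to 1.36. With equal arms, 52 to 95 events, and power = Φ(ln HR·√D/2 - 1.645) = 57% to 45%. Restoring 80% would take 24.73/(ln HR)² = 98 to 258 events.

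**The case against.** Including all-cause death is a legitimate choice, since it avoids treating death as uninformative censoring. That stands: the error is a margin derived without deaths, not the composite itself.

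A reader might infer that non-inferiority becomes too easy under any reading. The documents do not support that. The margin is defined in absolute terms, with HR 2.02 given as its equivalent; on the absolute scale equal deaths mainly cost precision, and the 95% wording becomes stricter. The anti-conservative effect belongs to the HR scale. The log-rank test and HR confidence limit in section 16.2.2 make that the most likely operative scale.

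A reader might also call 21-69% the type I error of the protocol's own hypothesis. It is not, because that hypothesis concerns the composite. It is the error against the invasive-only boundary from which the margin was derived.

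The size rests on an assumed mortality. The one figure in the protocol (section 1.1.5), "breast cancer accounting for only 20% of all deaths (2% breast deaths and 11% overall deaths", has no stated time frame and comes from a trial of excised DCIS not restricted to low-risk disease. It shows that most deaths there were not from breast cancer, but it does not give a rate for this trial. Women here must also be fit for surgery, and serious conditions that would prevent compliance exclude them (sections 4.1 and 4.2), so the upper end of the range is the least supported. The direction survives: 1% mortality at five years already gives about 15%. Equal deaths by arm is likewise an assumption.

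**Conclusion.** The mismatch is explicit and does not depend on any assumption: the endpoint includes deaths, while the control rate, margin, hazard ratio, events and sample size do not. As a result the three forms of the non-inferiority criterion disagree.

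The size is conditional. It requires the HR margin to be the operative one, deaths equal in both arms at 0.3-1.0% per year, exponential times and 839 evaluable women. The tolerated invasive-cancer HR is then about 2.6-4.0. It reaches three only at about 0.5% deaths per year, so a general claim of a three- to fourfold rate would go beyond the figures. The stated HR margin and 80% power are not valid for the endpoint as defined and need correction.

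**What to change.** Align endpoint and margin by amendment. Which endpoint is primary is the sponsor's choice.

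- **(a)** Apply the 2.5-point / HR 2.02 test to time to ipsilateral invasive breast cancer, with death as a competing event, and keep the composite as supportive. Restate the power: about 65% if both arms are at 97.5%. That shortfall from 80% arises because 932 reproduces only when the event probability is averaged over 97.5% and 95%, and not from removing deaths.
- **(b)** Keep the composite and restate the control rate with deaths included, the HR that matches 2.5 points (about 1.65-1.36 over the assumed range) and the power at the current sample size (about 57-45%). State the mortality assumption and its source.

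Under either option, name one form of the margin as the decision rule and drop or reconcile the other two.

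Cost: an amendment, matching text in the analysis plan, and a less favourable stated power. Restating needs no new data. Restoring 80% power under (b) would be a larger change, at about 98-258 events.

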2.2.2.2 Secondary Outcomes

- Time to development of ipsilateral invasive breast cancer: defined in whole days measured as time from randomisation until first report of ipsilateral invasive disease. Randomised patients with no evidence of disease will be censored at the last reported follow-up
- Time to development of any invasive breast cancer: defined in whole days measured as time from randomisation until first report of any invasive disease. Randomised patients with no evidence of disease will be censored at the last reported follow-up
- Time to development of contralateral invasive breast cancer: defined in whole days measured as time from randomisation until first report of contralateral invasive disease. Randomised patients with no evidence of disease will be censored at the last reported follow-up
- Overall survival time: defined in whole days measured as time from randomisation to date of death from any cause. Patients who withdraw or who are lost to follow-up will be censored at the date last known to be alive. Patients who remain alive during the course of the study will be censored at the date last seen alive
- Time to mastectomy: defined in whole days measured as the time from randomisation until time of mastectomy surgery. All other patients will be censored at last know follow-up assessment having not had a mastectomy

Page **7** of **48** Version 4.0, 15th March 2016

- Time to surgery: defined as time in whole days measured from randomisation until first reported ipsilateral breast cancer/DCIS related surgery. All other patients will be censored at last known follow-up assessment having not received surgery
- Quality of Life: will be assessed using the following:

Brief COPE

Spielberger State-Trait Anxiety Inventory

SF-36v2 Health Survey

Euro Qol EQ-5D

- Quality-adjusted Life years (QALY): survival time and longitudinal measures of EQ-5D will be combined to form a QALY outcome
- Costs and cost-utility: per-patient costs will be calculated from Patient Costs Questionnaires and
 utilising clinical data and key resource use data from Case Report Forms (CRFs), enabling economic
 evaluation of clinically important outcomes such as cost per additional surgical treatment avoided and
 cost per diagnosis of ipsilateral breast cancer and cost per QALY

3 TRIAL DESIGN

LORIS is a multi-centre, randomised (1:1), controlled phase III trial of surgery versus active monitoring in patients with low risk DCIS, incorporating a 2 year internal Feasibility Study, designed to answer the following question:

Can women with newly diagnosed low risk DCIS safely avoid surgery, without detriment to their psychological well-being and can those patients who require surgery be identified by pathological and radiological criteria?

Patients diagnosed locally with non-high grade DCIS will be registered with the Trial Office in order for the Central Histopathology Review team to verify that the patient has low risk disease. Patients with confirmed low risk disease will then be randomised to Surgery or Active Monitoring.

The LORIS Trial will seek to randomise 932 women with low risk disease. This is based on a non-inferiority margin defined as an absolute reduction in the 5 year ipsilateral invasive breast cancer free survival rate at 5 years of 2.5% i.e. from 97.5% to 95%.

4 ELIGIBILITY

The following criteria are applicable in order for a patient to be registered into the study. Patients will only be deemed eligible for randomisation following confirmation of low risk disease by the trial's Central Histopathology Review team.

4.1 Inclusion Criteria

- 1) Female, aged ≥ 46 years
- 2) Screen-detected or incidental microcalcification
- 3) Histologically confirmed diagnosis of non-high grade DCIS confirmed by local pathologist (for both breasts if bilateral disease) by:

Small volume core biopsy and Vacuum Assisted Core Biopsy (VACB)

Or

Vacuum Assisted Core Biopsy (VACB) alone as first line diagnostic approach

Or

Small volume biopsy or VACB plus open diagnostic surgical biopsy (without clear margins)

Or

Page 8 of 48 Version 4.0, 15th March 2016

Open diagnostic surgical biopsy (without clear margins)

(in accordance with the current NHSBSP Guidelines for Pathology Reporting in Breast Cancer Screening)

- 4) DCIS diagnosed ≤90 days before registration
- 5) Bilateral DCIS is permitted if non-high grade DCIS is confirmed in both breasts at the time of mammogram and diagnostic biopsy
- 6) Able to give informed consent and comply with the trial schedule and completion of Patient Reported Outcome questionnaires
- 7) Patient fit and willing to undergo surgery
- 8) Written informed consent obtained

4.2 Exclusion Criteria

- 1) Previous or current diagnosis of invasive breast cancer or previous ipsilateral DCIS (previous surgically treated contralateral DCIS is permitted)
- 2) A mass lesion clinically on imaging at the site of the microcalcification which has not been proven on biopsy to be a specific benign lesion
- 3) Surgical procedure with curative intent (even if clear margins have not been achieved)
- 4) Unequivocal comedo necrosis observed
- 5) Any serious and/or unstable pre-existing condition that would prevent compliance with the trial or the consent process
- 6) Recent onset ipsilateral blood-stained nipple discharge without benign explanation
- 7) High risk group for developing breast cancer (as defined in current NICE guidelines for familial breast cancer (42), or due to prior exposure to mantle field radiotherapy)

5 SCREENING AND CONSENT

Please see Flowchart 1: Patient Pathway to Randomisation, later in this section.

5.1 Involvement of Local Breast Unit or Screening Unit

It is expected that the majority of patients enrolling in the trial will have recently attended their local Breast Unit or Screening Unit.

Where possible, the Breast Unit or Screening Unit should supply potential patients with a copy of the brief Patient Information Leaflet, either with the invitation to attend for assessment or when attending for a biopsy.

5.1.1 Patient Information Leaflet

The aim of the Patient Information Leaflet is to describe DCIS to potential LORIS participants and to prepare the patient for the possibility of being invited to take part in a research study at an early stage in the patient pathway.

It is recognised from the experiences of the HTA funded ProTECT Trial that patients who are provided with trial information prior to learning of their diagnosis are more receptive and inclined to enter a clinical trial than those patients that have not received any trial information.

The LORIS Patient Information Leaflet has been carefully constructed with the assistance of Independent Cancer Patients Voice (ICPV) and has been ethically approved for use prior to the patient's diagnosis. Whilst it is appreciated that the information is provided to patients at a very early time-point and may not be relevant to all patients, patient interviews conducted during the feasibility phase of the LORIS Trial by the SHORE-C team indicated that patients are receptive to receiving the information at this stage in the pathway.

Page 9 of 48 Version 4.0, 15th March 2016

